## Section 7.6 Shipment of trial product to patient's home

For selected countries, and if permitted by local regulations, the investigator may offer to send trial product and auxiliaries from the trial site or pharmacy to the patient's home by courier service. *For these patients visit 2, 4, 6 and 8 may be conducted as a phone visit.*

## Section 8 Discontinuation/Withdrawal criteria

The patient may be discontinued at any time during the trial at the discretion of the investigator for safety, behavioural, compliance or administrative reasons.

Efforts must be made to have the patients, who discontinue trial product, attend EoT visit to collect the required data for the analysis of the primary (and confirmatory secondary) endpoint. Only patients who withdraw consent will be considered as withdrawn from the trial. Patients must be educated about the continued scientific importance of their data, even if they discontinue trial product.

*For patients shifting to commercial products see section 5.2.1.*

## Section 9.8.5 Haematology

Blood samples for analysis of haematology will be collected according to flowchart section 2. Only applicable during major surgery, haematology must be collected at the surgery day before ~~and after~~ the pre-operative loading dose of N8-GP and again after completion of surgery. ~~The sample taken post dose must not be taken from the same vein used for administration of N8-GP~~

Protocol Amendment no 2  
Trial ID: NN7088-4410

~~CONFIDENTIAL~~

Date:  
Version:  
Status:  
Page:

18 June 2019  
1.0  
Final  
5 of 5

**Novo Nordisk**

### **Appendix 3 – Trial governance considerations**

#### ***15) Web-portal for document exchange***

*During the trial a web-portal will be used for document exchange between Novo Nordisk and the sites. The web-portal is not an archiving tool but could be used as a temporary archiving place during the trial as judged by the investigator.*

1.1 Trial information

In the following, a brief description of the trial is presented. Please go to the protocol for further details.

Rationale:

The rationale for performing this trial is to allow the continued evaluation of the safety and efficacy of turoctocog alfa pegol in order to obtain additional data on long-term use. Introducing a twice or three times weekly prophylactic dosing regimen to the majority of patients is intended to show potential improvement in clinical outcomes by converting patients to a milder bleeding phenotype. Joint health and target joints will be assessed and evaluated at inclusion and at end of trial.

Objectives and endpoints:

Primary objective

To investigate the safety of turoctocog alfa pegol during continuous use for prevention and treatment of bleeding episodes of previously turoctocog alfa pegol treated severe haemophilia A patients.

Secondary objectives

To investigate the following in severe haemophilia A patients previously treated with turoctocog alfa pegol

- Development of FVIII inhibitors
- Efficacy of turoctocog alfa pegol prophylaxis
- Haemostatic efficacy of turoctocog alfa pegol when used for treatment of bleeds

Overall design:

This phase 3 trial is a multi-centre, multi-national, open-label, non-randomised trial evaluating safety and efficacy of turoctocog alfa pegol during prophylaxis treatment and treatment of bleeds. There will be three turoctocog alfa pegol treatment arms (dosing once weekly, twice weekly, and three times weekly) and no comparator.

1.2 Scope of the statistical analysis plan

This SAP is based on the protocol *Safety and Efficacy of turoctocog alfa pegol (N8-GP) in Prophylaxis and Treatment of Bleeds in Previously N8-GP Treated Patients with Severe Haemophilia A*, version 1.0.

Statistical Analysis Plan
Trial ID: NN7088-4410
UTN: U1111-1202-2780
EudraCT No.: 2017-003788-36

~~CONFIDENTIAL~~

Date: 10 September 2020
Version: 2.0
Status: Final
Page: 5 of 11

Novo Nordisk

2 Statistical considerations

Novo Nordisk will be responsible for the statistical analyses.

2.1 Sample size determination

All patients participating in NN7088-3859 (pathfinder2) or NN7088-3885 (pathfinder5) fulfilling the inclusion and exclusion criteria of this trial will be eligible to participate where continuous safety assessments will be made. Given that at least 150 patients participate in this trial, the background incidence rate could be up to 0.02 for a given adverse event that was not observed, i.e. the 95% upper bound on the rate of occurrence is 0.02.

2.2 Definition of analysis sets

In general, safety endpoints will be reported for Safety Analysis Set while efficacy endpoints will be reported for Full Analysis Set (FAS). These analysis sets are described below.

The patients or observations to be excluded, and the reasons for their exclusion must be documented before database lock. The patients and observations excluded from analysis sets, and the reason for this, will be described in the clinical trial report.

Safety analysis set

All patients enrolled in the trial have previously been exposed to trial product and therefore all enrolled patients will be included in the Safety Analysis Set. The trial patients will be analysed according to the received treatment.

Full analysis set

All patients exposed to at least one dose of trial product in the current trial will be included in the Full Analysis Set. The trial patients will be analysed according to the received treatment.

Exceptional outlier plasma activities may be excluded when analysing pharmacokinetic-related endpoints based on the FAS. Default rules for exclusion are described in the paragraph on pre-dose FVIII activity level. Decision to exclude additional FVIII activity measurements from analysis based on the FAS may be made during a review prior to database lock according to ICH-E9, and it will be the joint responsibility of the clinical pharmacology scientist and the trial statistician to decide upon this. The observations to be excluded from the FAS and the reason for their exclusion will be documented and signed by the clinical pharmacology scientist and the trial statistician as part of the database lock minutes. This will also be described in the clinical trial report. The documentation will be stored together with the remaining trial documentation.

Statistical Analysis Plan
Trial ID: NN7088-4410
UTN: U1111-1202-2780
EudraCT No.: 2017-003788-36

CONFIDENTIAL

Date:	10 September 2020	Novo Nordisk
Version:	2.0	
Status:	Final	
Page:	6 of 11	

2.3 Statistical analyses

If necessary, a statistical analysis plan (SAP) may be written in addition to the protocol, including a more technical and detailed elaboration of the statistical analyses. The SAP will be finalised before database lock.

2.3.1 Primary endpoint

Number of adverse events reported

All reported adverse events (AEs) will be considered treatment emergent adverse events since all patients had been treated with N8-GP in other pathfinder trials prior to participation in this trial. All AEs, serious adverse events (SAEs) and adverse events of special interest (AESIs) will be summarised by frequency of events and frequency of patients with any event. Furthermore, all AEs will be summarised by severity and causal relation to trial product. In addition, listings will be provided displaying all AEs, SAEs and AESIs.

2.3.2 Secondary endpoints

For all endpoints based on bleeding episode data, only bleeding episodes treated with N8-GP will be included.

Multiple bleeding locations occurring from the same event (e.g. due to a bicycle accident) or at the same time point will be counted as one bleeding episode.

A re-bleed is defined as a worsening of symptoms in the same location after an initial period of improvement, either on treatment or within 72 hours after completed treatment. If a bleeding episode occurs in the same location later than 72 hours after completed treatment it is considered a new bleeding episode.

2.3.2.1 Supportive secondary endpoints

Incidence of FVIII inhibitors ≥ 0.6 BU

The number of inhibitor patients will be reported and all inhibitor data will be presented.

Number of bleeding episodes on prophylaxis

The ABR of treatment requiring bleeding episodes will be estimated by a Poisson regression model with logarithmic prophylaxis duration as offset and allowing for over-dispersion. Over-dispersion will be estimated as Pearson's chi-square statistic divided by the degrees of freedom. The estimated ABR will be presented together with a two-sided 95% confidence interval. For sub-groups with no bleeds or less than 5 patients, the 95% confidence interval will not be presented. A sensitivity analysis based on a negative binomial regression model with number of bleeding episodes requiring treatment as the outcome variable, and adjusting for exposure time will also be performed.

Statistical Analysis Plan
Trial ID: NN7088-4410
UTN: U1111-1202-2780
EudraCT No.: 2017-003788-36

~~CONFIDENTIAL~~

Date:	10 September 2020	Novo Nordisk
Version:	2.0	
Status:	Final	
Page:	7 of 11	

The analysis of ABR will be repeated as a sensitivity analysis to investigate the potential impact of early withdrawals by imputing number of bleeding episodes for withdrawals. For patients withdrawing prematurely, the number of bleeding episodes counting in the analysis will be imputed up to what they could be expected to have had if they had completed the trial. If e.g. a patient withdraws after 12 months with 5 bleeding episodes, but the patient should have been in the trial for 24 months, then this patient will in the sensitivity analysis count as having had 10 bleeding episodes in 24 months. This is similar to LOCF and will prevent a downwards bias in ABR caused patients with many bleeding episodes withdrawing early. If a patient changes from once weekly to one of the more frequent dosing frequencies, then when doing the sensitivity calculation for once weekly, bleeds during time on the more frequent dosing is calculated using LOCF based on the previous period on every seven day dosing. This is also the case if a patient changes from every seven day dosing more than once, i.e. for each period on more frequent dosing the bleeds for every seven day dosing is imputed based on the previous consecutive period on every seven day dosing.

ABR for each treatment regimen (once weekly, twice weekly, and three times weekly) will be estimated by age group (0-5 years, 6-11 years, 12-17 years and 18- years).

ABR will also be estimated by doing the following further sub-groupings:

- Cause of bleed (spontaneous and traumatic)
- Location of bleed. No sensitivity analyses will be done for this sub-grouping (neither using negative binomial modelling nor using imputation).
- Country. No sensitivity analyses will be done for this sub-grouping (neither using negative binomial modelling nor using imputation).
- Race. No sensitivity analyses will be done for this sub-grouping (neither using negative binomial modelling nor using imputation).
- Ethnicity. No sensitivity analyses will be done for this sub-grouping (neither using negative binomial modelling nor using imputation).
- Month in trial. No sensitivity analyses will be done for this sub-grouping (neither using negative binomial modelling nor using imputation).
- Time since last dose (0-24 hours, 24-48 hours, 48-72 hours and >72 hours). No sensitivity analyses will be done for this sub-grouping (neither using negative binomial modelling nor using imputation).

Number of spontaneous bleeding episodes on prophylaxis

Included in the above description of ABR by cause of bleed.

Haemostatic effect of N8-GP when used for treatment of bleeding episodes assessed as: Excellent, Good, Moderate, or None

Haemostatic effect will for each treatment regimen (once weekly, twice weekly, and three times

Statistical Analysis Plan
Trial ID: NN7088-4410
UTN: U1111-1202-2780
EudraCT No.: 2017-003788-36

~~CONFIDENTIAL~~

Date:	10 September 2020	Novo Nordisk
Version:	2.0	
Status:	Final	
Page:	8 of 11	

weekly) be summarised by age group (0-5 years, 6-11 years, 12-17 years and ≥ 18 years).

Haemostatic effect will be summarised according to:

- Response expressed as excellent, good, moderate, none.
- Success or failure, where success will be defined as a response of good or excellent and failure will be defined as moderate, none or missing
- Success or failure after exclusion of bleeds with missing evaluation of haemostatic response, i.e. success will be defined as a response of good or excellent and failure will be defined as moderate or none information.

Furthermore, success rates will be estimated with 95% confidence intervals using logistic regression accounting for repeated measures within patient assuming compound symmetry working correlation. Age group will be included as a factor and modelling done separately for each treatment regimen. This estimation will be done both including missing haemostatic evaluations as failures and excluding missing evaluations.

Summaries will also be done for the following further sub-groupings:

- Cause of bleed (spontaneous and traumatic). Estimation of success rates and 95% confidence intervals using above described modelling will also be performed (both including missing as failures and excluding missing).
- Location of bleed.
- Severity.
- Country.
- Race
- Ethnicity

Number of N8-GP injections required per bleeding episode

This endpoint will be summarised and listed.

Pre-dose FVIII activity levels for patients on N8-GP prophylaxis

The following rules will be implemented for FVIII pre-dose and post-dose activity to ensure data representing steady-state on a given treatment regimen:

- FVIII activity data prior to the 4th prophylaxis dose will be excluded for each switch in treatment regimen
- FVIII activity data will be excluded if post-dose activity is \leq pre-dose FVIII activity
- FVIII activity data will be excluded if post-dose sample is taken more than 90 minutes after dosing
- FVIII activity results will be excluded for plasma samples defrosted during transit.

Statistical Analysis Plan
Trial ID: NN7088-4410
UTN: U1111-1202-2780
EudraCT No.: 2017-003788-36

~~CONFIDENTIAL~~

Date:	10 September 2020	Novo Nordisk
Version:	2.0	
Status:	Final	
Page:	9 of 11	

The pre-dose FVIII activity levels will be modelled to get an estimate of the pre-dose level for N8-GP at steady-state. The model will be a mixed model on the logarithmic plasma activity levels with age as a factor and patient as a random effect. Separate modelling will be performed for each treatment regimen. Plasma concentrations below lower limit of quantification (LLOQ) will be set to half the value of the LLOQ. The estimated pre-dose FVIII level will be presented together with the 95% confidence intervals.

A sensitivity analysis will be performed including all activity results except activities measured in relation to the first 4 prophylaxis doses after switch of treatment regimen.

Pre-dose activity will furthermore be summarised by visit and treatment regimen.

Change in joint health status from start to end of trial

Target joint status is assessed at inclusion in trial. For intervals of 12 months, the number of baseline target joints with 0, 1, 2,... number of bleeds is presented.

Haemostatic response during major surgical interventions

The endpoint of assessment of haemostatic effect during major surgical intervention (excellent, good, moderate or none) will be summarised and listed.

Change from baseline till end of trial in treatment satisfaction (Hemo-SAT)

Data will be scored according to established scoring algorithms (where applicable) and changes from first assessment (at screening/V1) to last assessment (at EoT visit) will be summarised and listed using descriptive statistics. Further analysis will be performed separately by Novo Nordisk Health Economics Department.

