### 8.1 Discontinuation of trial treatment

The patient must be discontinued from trial product, if the following applies:

1. Included in the trial in violation of the inclusion and/or exclusion criteria
2. Lack of haemostatic effect of the trial product. The bleed is not controlled after 48 hours of appropriate turoctocog alfa pegol treatment
3. FVIII inhibitor (>5 BU) as confirmed by re-testing by Central Laboratory
4. Allergy/anaphylaxis to the trial product requiring systemic treatment
5. Treatment with other FVIII containing products other than trial product turoctocog alfa pegol or anti-coagulants (therapeutic doses)
6. Incapacity or unwillingness to follow the trial procedures
7. FVIII inhibitor ( $\geq 0.6$  and  $\leq 5$  BU) as confirmed by re-testing by Central Laboratory that makes treatment (prophylaxis and/or treatment of bleeding episodes) with turoctocog alfa pegol clinically ineffective
8. Simultaneous participation in another clinical trial of an approved or non-approved investigational medicinal product.
9. Applicable for France only; In the case of a major thromboembolic event (e.g. myocardial infarction, cerebrovascular disease or deep venous thrombosis) as per investigator.

See the flowchart for data to be collected at the time of treatment discontinuation and follow-up and for any further evaluations that need to be completed.

The primary reason for discontinuation of trial product must be specified in the EoT form in the eCRF, and final drug accountability must be performed. A treatment discontinuation session must be made in the IWRS.

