**Table 9-4 Definition of haemostatic effect of N8-GP when treating bleeding episodes**

Category	Definition
Excellent	Abrupt pain relief and/or unequivocal improvement in objective signs of bleeding within approximately 8 hours after a single injection
Good	Definite pain relief and/or improvement in signs of bleeding within approximately 8 hours after an injection, but possibly requiring more than one injection for complete resolution
Moderate	Probable or slight beneficial effect within approximately 8 hours after the first injection; usually requiring more than one injection
None	No improvement or worsening of symptoms

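### Re-bleeds are defined but used in no endpoint, so a bleed that improves early and then re-bleeds can still count as a haemostatic success

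*SAP*

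**What the plan says.** **Re-bleeds.** SAP 2.3.2 states: "A re-bleed is defined as a worsening of symptoms in the same location after an initial period of improvement". The window covers the treatment itself and the 72 hours that follow its completion. The section continues: "If a bleeding episode occurs in the same location later than 72 hours after completed treatment it is considered a new bleeding episode". Protocol 10.3.2 has the same rule. By implication, anything earlier at that site belongs to the index episode. Neither document uses the term again.

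**Success.** SAP 2.3.2.1 and protocol 10.3.2.1 give one rule: "Success or failure, where success will be defined as a response of good or excellent and failure will be defined as moderate, none or missing". A variant leaves out bleeds with a missing rating. Both versions are modelled by logistic regression, separately for each regimen, with age group as a factor.

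**The rating.** Protocol Table 9-4 defines Excellent as "Abrupt pain relief and/or unequivocal improvement in objective signs of bleeding within approximately 8 hours after a single injection". Good has the same time anchor and allows further injections. None covers symptoms that fail to improve or that get worse, and has no time anchor.

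**Uncontrolled bleeds.** Discontinuation criterion 2 in protocol 8.1 reads: "Lack of haemostatic effect of the trial product. The bleed is not controlled after 48 hours of appropriate turoctocog alfa pegol treatment". The success rule does not refer to it.

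**Bleed counts.** "The ABR of treatment requiring bleeding episodes will be estimated by a Poisson regression model" (SAP 2.3.2.1). How re-bleeds enter that count is not written out.

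**The concern.** The two ratings that count as success describe the first hours after an injection. A re-bleed by definition comes after an improvement, so re-bleeds will tend to arise in bleeds that already meet the wording for Good or Excellent. Take a knee bleed that improves at 6 hours, worsens at 40 hours and needs more doses. It is one episode, and under the success rule it can enter the analysis as one success. A bleed rated Good at about 8 hours and still uncontrolled at 48 hours can do the same.

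The synopsis lists haemostatic effect among the key secondary endpoints, and readers will take the success rate as the proportion of bleeds that were controlled. As defined, it may only be the proportion that improved early. No planned output identifies the re-bleeds, so a reader of the trial report could not tell how far the two differ.

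**Working it through.** The plan states no figure for re-bleeding or for an expected success rate, so there is nothing of its own to reproduce. The check has three parts.

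**1. Can a re-bleeding episode stay a success?**
- Improvement at 6 hours satisfies the wording of Excellent or Good in Table 9-4. If more doses rule out Excellent, Good remains, and Good is also a success.
- Later worsening also fits None, which is a failure.
- The two readings give opposite results. Protocol 9.5.1 asks for a haemostatic evaluation of each treated bleed but gives no time at which it is fixed and no rule for revising it.
- Table 9-1 sets the stop time at the first signs that the bleed is ceasing, not at full resolution. A bleed can thus be recorded as stopped before it re-bleeds. If the re-bleed is entered as its own record, one analysed episode may carry two ratings, with no rule for choosing between them.
- Direction: counting re-bleeds as failures can only move a bleed from success to failure. The resulting rate cannot exceed the rating-only rate.

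**2. How large could the shift be?**
Inputs: *s* is the success rate that protocol 3.2.3 quotes, 84.2% for pathfinder2 and 78.6% for the main phase of pathfinder5. *r* is the share of rated successes that re-bleed. The documents do not give *r*, so a range is assumed. Formula: *s* × (1 − *r*).

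| Assumed *r* | From 84.2% | Drop (points) | From 78.6% | Drop (points) |
|---|---|---|---|---|
| 1% | 83.4% | 0.8 | 77.8% | 0.8 |
| 2% | 82.5% | 1.7 | 77.0% | 1.6 |
| 5% | 80.0% | 4.2 | 74.7% | 3.9 |
| 10% | 75.8% | 8.4 | 70.7% | 7.9 |

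For example, 0.842 × 0.95 = 0.800. If every re-bleeding episode is already rated Moderate or None, *r* is 0 and nothing changes. Bleeds falling under criterion 2 are not in this table.

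**3. How does that compare with the precision?**
- Exposure is at most 170 patients (protocol 5.2) × 2 years = 340 patient-years.
- With the ABRs of 2.13 and 3.70 quoted in protocol 3.2.3, that gives 340 × 2.13 = 724 to 340 × 3.70 = 1,258 bleeds.
- The 95% half-width is 1.96 × √(0.842 × 0.158 × DE / n), with an assumed design effect DE of 1 to 2 for repeated bleeds in a patient. With n = 1,258 and DE = 1 it is 2.0 points; with n = 724 and DE = 2 it is 3.8 points.
- From 84.2%, the drop at *r* = 2% (1.7 points) lies inside that half-width. The drops at 5% and 10% (4.2 and 8.4 points) lie outside it.
- This pooled interval is the narrowest case. The plan models each regimen separately, and exposure will fall short of 340 patient-years because protocol 5.2 expects 153 completers and 5.2.1 allows early completion. With an assumed 100 bleeds in a group, the half-width is 7.1 points (DE = 1) to 10.1 points (DE = 2), which covers most or all of the range.

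**The case against.** A reader might infer more than this: that a re-bleed definitely leaves the index bleed a success, that it vanishes from the ABR and from every output, and that the success rate is therefore overstated. The documents do not support that reading.

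- **The plan is silent on the rating; it does not state a wrong rule.** None includes worsening with no time limit, so an investigator could properly rate a re-bleeding episode as a failure. An overstatement arises only where such bleeds keep a Good or Excellent rating. This stands, and it is why the conclusion says *can be*. It does not remove the problem, because the opposite rating is equally open.
- **The ABR does not lose a bleed.** The index episode is counted once, and merging the re-bleed into it is a counting convention. Counting re-bleeds separately at 2%, 5% or 10% per bleed would move an ABR of 3.70 to 3.77, 3.89 or 4.07. That is the size of the convention, not of an error. This stands.
- **Re-bleeds leave some trace.** Protocol 7.1.2 assigns all doses given for an episode to that bleed, so they enter injections per bleed. Discontinuation under criterion 2 is recorded as a reason in the eCRF. This stands, but neither record marks a re-bleed or alters a success.
- **The stakes are limited.** SAP 2.3.2.1 files the endpoint under supportive secondary endpoints, there is no comparator, and no test is planned on it. Counting missing ratings as failures pulls the other way. That is a separate route, though, and the variant that excludes missing ratings does not have it.
- **Derivation is imperfect.** Protocol 9.5.1 lists no re-bleed item and no time of worsening. Start, stop and dose times cannot reliably separate an on-treatment re-bleed from a Good response that needed several injections. This stands and belongs in the fix.

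**Conclusion.** The point holds in conditional form. The plan defines a re-bleed, implicitly merges it into the index bleed, and then gives it no role. Because success rests on a rating anchored at about 8 hours, with no rule on when that rating is final, bleeds that re-bleed or are uncontrolled at 48 hours can be reported as successes. Any error from this source runs in favour of the product.

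Its size cannot be settled from the documents. Under assumed re-bleed shares of 1% to 10% of rated successes, the fall is 0.8 to 8.4 points from 84.2%, or 0.8 to 7.9 points from 78.6%. It is zero if re-bleeding bleeds are already rated as failures. Whether a shift would exceed the confidence interval depends on the unknown share and on the size of each regimen group, so no claim about that should be made. This is more than missing detail, because following the written rule can give a favourable result for bleeds that were not controlled. It does not affect the primary safety endpoint.

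**What to change.** In protocol 10.3.2.1 and SAP 2.3.2.1:

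1. Keep the rating-only success rate, which allows comparison with pathfinder2 and pathfinder5.
2. Add a supplementary success analysis with the same model. Count as a failure, whatever the first rating, any bleed with a re-bleed as defined in protocol 10.3.2 and any bleed leading to discontinuation under criterion 2.
3. Report the number and percentage of re-bleeds by regimen.
4. State that a re-bleed adds no count to the ABR.
5. Derive the re-bleed flag from the location and timing records that the 72-hour rule already requires. State that on-treatment re-bleeds may be only partly identifiable, because no re-bleed item or time of worsening is recorded.

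The cost is a few sentences, a derived flag and an extra table, settled before database lock. No new data collection is needed, and no clinical rule changes. SAP section 3, which now declares no departures from the protocol, must record the addition if only the SAP is changed. The downsides are a somewhat lower figure beside the existing one, and a flag that may miss some on-treatment re-bleeds, so the supplementary rate may still be too high.

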#### **Incidence of anti-PEG binding antibodies**

Number of positive/negative samples will be summarised by visit and listed. Furthermore, plots will be created of incremental recovery according to PEG antibody status at baseline and during the trial. Rules for exclusion of FVIII activity measurements are as defined in the paragraph on: "Pre-dose FVIII activity levels on N8-GP prophylaxis".

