2.3.3 Exploratory endpoint

Incidence of anti-N8-GP binding antibodies

Number of positive/negative samples will be summarised by visit and listed.

Incidence of anti-PEG binding antibodies

Number of positive/negative samples will be summarised by visit and listed. Furthermore, plots will be created of incremental recovery in relation to PEG antibody status at baseline and during the trial. Rules for exclusion of FVIII activity measurements are defined in the paragraph: "Pre-dose FVIII activity levels for patients on N8-GP prophylaxis".

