2.5 Additional efficacy related tables/figures/listings

Post-dose activity measurements will be modelled and presented in the same forms as pre-dose activity measurements, see section on “Pre-dose FVIII activity levels on N8-GP prophylaxis”.

Incremental recovery is defined as post-dose FVIII activity minus pre-dose FVIII activity and divided by the administered dose. Incremental recovery will be summarised by visit and listed.

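### The anti-PEG plots of incremental recovery leave out every pre/post pair with observed recovery of zero or less, which is selection on the quantity plotted

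*SAP*

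**What the plan says.** Incremental recovery is defined in SAP 2.5 (same definition in protocol 10.5): "Incremental recovery is defined as post-dose FVIII activity minus pre-dose FVIII activity and divided by the administered dose".

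For the anti-PEG endpoint, SAP 2.3.3 states that "plots will be created of incremental recovery in relation to PEG antibody status at baseline and during the trial". It adds: "Rules for exclusion of FVIII activity measurements are defined in the paragraph" on pre-dose FVIII activity. Protocol 10.3.3 has the same cross-reference: "Rules for exclusion of FVIII activity measurements are as defined in the paragraph on" pre-dose FVIII activity.

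That paragraph (SAP 2.3.2.1, protocol 10.3.2.1) gives the purpose and scope of its rules: "The following rules will be implemented for FVIII pre-dose and post-dose activity to ensure data representing steady-state on a given treatment regimen". There are four. Three concern data before the fourth dose after a regimen switch, late post-dose samples, and samples thawed in transit. The remaining one is at issue here: "FVIII activity data will be excluded if post-dose activity is" no higher than pre-dose activity.

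The same paragraph handles low values as follows: "Plasma concentrations below lower limit of quantification (LLOQ) will be set to half the value of the LLOQ". It also plans a sensitivity analysis that brings back all activity results except those around the first four doses after a switch. That analysis is described for the pre-dose model.

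**The concern.** Three of the four rules do not look at the recovery result. The fourth does: whether a pair is kept depends on the sign of the quantity to be plotted. It is also not a steady-state criterion. A post-dose value that fails to exceed the pre-dose value points either to a sampling, labelling or dosing error or to absent recovery, and the rule does not tell these apart.

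The protocol treats low recovery as informative. Section 9.8.8.1 lists recovery below expected among the reasons to suspect an inhibitor, and requires recovery of at least 66% of expected before a confirmed inhibitor counts as gone. If anti-PEG antibodies removed the product's effect in some patients, the most extreme results would be the ones left out of the only display that sets recovery against anti-PEG status.

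**Working it through.** The documents give no figure on this point, so there is none to reproduce. The check is algebra, a simulation on assumed inputs, and a comparison with the other planned outputs.

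**Step 1: what the rule removes.** Write IR = (post − pre)/dose, from SAP 2.5, with dose > 0. Then post ≤ pre ⇔ post − pre ≤ 0 ⇔ IR ≤ 0. The plot can contain only IR > 0. This needs no assumption.

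**Step 2: which true recoveries are affected.** The documents give neither the assay error, nor the lower limit of quantification (LLOQ), nor the expected rise. Assumed inputs:
- dose 50 IU/kg, with a full rise of 50, 100 or 150 IU/dL (IR of 50/50 = 1, 100/50 = 2 or 150/50 = 3)
- pre-dose activity 0.5 or 3 IU/dL, LLOQ 1 IU/dL
- log-scale assay SD 0.10 or 0.20
- values below the LLOQ set to LLOQ/2 in both samples

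With 400,000 simulated pairs per setting, the share excluded (range over rise and assay SD) is:

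| True recovery | Pre-dose 0.5 (below LLOQ) | Pre-dose 3 (measurable) |
|---|---|---|
| None | about 100% | about 50% |
| 2% of full | 0 to 2.1% | 0 to 15.6% |
| 10% of full or more | 0% | 0% |

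In the first column, both samples of a zero-recovery pair become LLOQ/2 = 0.5. They tie, and the pair is dropped. In the second column, assay noise alone decides which sample is higher, so about half the pairs survive. Those survivors have a mean IR of about 0.007 to 0.014, against about 1 to 3 for full recovery. They appear as points close to zero.

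**Step 3: what this does to the plot.** Suppose the antibody-positive group has 10 pairs, of which k have observed IR ≤ 0 and the rest are normal. The plot shows 10 − k points:
- k = 1: 9 points
- k = 3: 7 points
- k = 5: 5 points
- k = 10: none

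Every point shown is normal whatever the value of k, and nothing on the plot reports k. These k values are illustrative.

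**Step 4: whether another output fills the gap.**
- The sensitivity analysis in SAP 2.3.2.1 restores excluded values for the pre-dose model. SAP 2.5 says post-dose activity is presented in the same forms, which may extend the analysis to post-dose activity. Nothing extends it to the anti-PEG plots.
- SAP 2.5 summarises incremental recovery by visit and lists it. It does not say whether the exclusions apply, and it does not split by antibody status.
- SAP 2.3.3 summarises antibody samples by visit and lists them, without recovery.
- SAP 2.2 requires excluded observations and reasons to be documented before database lock and described in the report, but not by antibody status.

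**The case against.** The plot is descriptive and belongs to an exploratory endpoint, with no test, model or decision attached. Its purpose is not stated, so that it should reveal loss of recovery is an inference, though a natural one. The rule is prespecified, is written for both pre- and post-dose activity, and has a sensible data-quality reading, because a swapped or missed sample is a credible cause of post ≤ pre. All of this stands. It limits the weight of the point but does not change what the rule removes.

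A reader might infer more than the documents support:
- **That total loss of recovery can never appear.** This is strict only for observed IR ≤ 0. With measurable pre-dose activity, some zero-recovery pairs remain as near-zero points, and partial loss is shown in full.
- **That all complete-loss pairs are deleted.** That result needs both samples below the LLOQ and the LLOQ/2 convention. The convention is written for the pre-dose model, and neither document says it governs incremental recovery.
- **That whole visits or patients disappear.** Only FVIII activity data are excluded. The patient stays in the antibody listings, all inhibitor data are presented, and listings can be matched by hand.
- **That the plot would hide a fall of some given percentage in mean recovery.** No mean is planned for it, and the documents give no rate of post ≤ pre pairs and no evidence that anti-PEG antibodies cause complete loss.

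**Conclusion.** The point holds for the anti-PEG recovery plots. By definition they are cut to recovery above zero, and no stated sensitivity analysis restores the missing pairs there. The selection is concentrated on complete or near-complete loss: about 50% to 100% of zero-recovery pairs under the assumed inputs, and essentially none at 10% of full recovery or above.

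The direction of any bias is toward no antibody effect, provided some excluded pairs reflect true loss and that loss is more common in antibody-positive patients. If every such pair were a handling error unrelated to antibodies, the rule would not create a difference or hide one. The number of affected pairs is unknown, so the size of the bias cannot be stated. The primary endpoint, inhibitor incidence and the bleeding-rate analyses are untouched. The change is worth making because this is the only planned output relating recovery to anti-PEG status and it is cheap to correct.

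**What to change.** 1. In SAP 2.3.3 and protocol 10.3.3, state that the post ≤ pre exclusion is not applied automatically to the anti-PEG recovery plots. The other three rules can stay.
2. In SAP 2.5 and protocol 10.5, state that it does not apply to the incremental recovery summary and listing either.
3. Remove such a pair only for a documented sampling, labelling or dosing error, through the pre-lock review already set up in SAP 2.2 and signed by the clinical pharmacology scientist and the trial statistician.
4. Plot every other such pair at its observed value, negative values included, with a flag. Do not reset negatives to zero. State how pairs with both samples below the LLOQ are shown.
5. Report the number of such pairs by anti-PEG status, both removed and retained.

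The rule may stay for the pre-dose and post-dose steady-state models. SAP section 3 declares no change from the protocol, so it needs a line if only the SAP is revised. The cost is wording and a plot flag. The downside is that a few undetected sample swaps may remain as flagged points.
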